18.7 Subgroup Analyses

Pre-specified subgroup analysis will include comparison of the effect of therapy in patients with:

- 1. LV mass index above and below the median at entry into the study.
- 2. Estimated PASP above and below the median at entry into the study
- 3. Dose of sildenafil achieved
- 4. Presence of atrial fibrillation
- 5. Differences in background therapy

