18. STATISTICAL CONSIDERATIONS

18.1 Sample Size and Power Considerations

18.1.1 Primary endpoint: Change in peak VO₂ (\triangle VO₂)

No previous study has characterized the standard deviation of the ΔVO_2 in a study population similar to that planned here where DHF patients are studied and strict entry criteria and a screening cardiopulmonary exercise test (CPXT) are used to minimize enrollment of patients with non-cardiac dyspnea and select for patients who can perform near maximal exercise (RER≥1.0). Patients who are unwilling or unable to perform at this level of exercise will not be eligible for enrollment. This requirement will reduce variability in both the primary endpoint (Δ peak VO₂) and the secondary endpoint measuring submaximal exercise (\alpha 6MW). Recognizing the lack of data relevant to the planned study population, we have based power calculations on the SD for the ΔVO_2 observed in randomized clinical trials (RCT) in SHF where ΔVO₂ was a primary (SD=2.7 ml/kg/min)¹¹¹ or secondary (SD≈2.7 ml/kg/min) ^{112,113} endpoint and on limited RCT data in DHF⁵⁰ (SD=1.3 ml/kg/min; [name], personal communication). A range of withdrawal due to death at 6 months was also estimated based on a large RCT in DHF (<2%)⁴⁷ and community based observational studies in DHF (13-16%)^{7,11}.

Power	85% Power			90% Power			analysis indicates that a sar	
	TE = 1.0 ml/kg/min	nin ml/kg/min	ml/kg/min ml/	TE = 1.0 ml/kg/min 172	TE = 1.2 ml/kg/min 120	TE =1.5 ml/kg/min	1.2 ml/kg/min in ΔVO_2 with	
SD=2.0	146					78		
SD=2.5	228	158	102	266	186	120	SD of ΔVO_2 =2.5 ml/kg/min. account for up to 25% mis	
SD=3.0	326	228 146	382	266	172	data, the projected sample s		
							is approximately 215 patients In patients with SHF, a si dose of sildenafil resulted in	

The relationship between power, effect size (mean difference in ΔVO_2) and SD of the ΔVO_2 using a two sample t-test and a two-sided alpha of 0.05 is shown in the table assuming 85% and 90% power. This

dose of sildenafil resulted in statistically significant increases in

TE=treatment effect (difference in Δ in peak VO2); SD = standard deviation of Δ in peak VO2

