18.2 Analysis Policies

A statistical analysis plan will be completed before the data are analyzed in an unblinded fashion. Due to clinical interest in departures from both sides of the null hypothesis, all test statistics will be twosided. The trial results will be reported according to guidelines specified in the CONSORT statement^{121,122}. A flow diagram describing screening, recruitment, randomization, dropout, and vital status will be included in the primary manuscript. Adverse events and efficacy data will be presented by the two treatment groups. Adherence, dropout, and lost-to-follow-up will be carefully examined across the two treatment groups. Analyses of safety will be based on data from all randomized patients who received at least 1 dose of study drug. All primary analyses will be based on intent-to-treat (ITT) principles using all randomized participants.

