18.2.1 Controlling Type-I Error

The primary endpoint of change in peak VO2 from baseline to 24 weeks will be evaluated at the twosided 0.05 level. A conservative approach will be taken with the multiple analyses on key clinical subgroups. For subgroup analyses, a significance level of 0.001 will be required for statistical significance. Thus, subgroup analyses will be considered exploratory unless the p-value from an interaction test is smaller than 0.001.

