18.4 Statistical Comparisons of Baseline Factors

For continuous variables, baseline factors will be compared across groups using mean (standard deviation) and median (25th and 75th percentiles) summary measures. For categorical variables, baseline factors will be summarized using counts and percentages with statistical comparisons based on the Pearson's chi-square statistic. Given the size of this proof of concept trial, the potential for inequitable distributions of baseline characteristics between the treatment groups exists. We have pre-specified subgroup analysis for those variables most likely to impact response to PDE-5 inhibition. Randomization will be stratified by site and by rhythm (presence of atrial fibrillation), primarily to insure that there are equal numbers of sildenafil and placebo treated patients in the group without atrial fibrillation who will undergo MRI. If significant differences in baseline characteristics exist, an analysis adjusted for these characteristics will be performed.

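### The subgroup tests for LV mass index and PASP split continuous baseline measures at the sample median, which costs power under a strict p<0.001 rule if the effect changes gradually

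*Protocol*

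**What the plan says.** Protocol section 18.7 lists five pre-specified subgroup comparisons, and section 2 gives the same list. The first two are "LV mass index above and below the median at entry into the study" and "Estimated PASP above and below the median at entry into the study". Section 18.2.1 sets the decision rule: "subgroup analyses will be considered exploratory unless the p-value from an interaction test is smaller than 0.001". Section 18.2 adds that "all test statistics will be twosided".

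Section 18.4 explains why these factors were chosen: "We have pre-specified subgroup analysis for those variables most likely to impact response to PDE-5 inhibition". Hypertrophy and pulmonary pressure are also two of the mechanisms argued in sections 5.1 and 5.3.

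Both modifiers are measured on a continuous scale. LV mass comes from traced MRI images, taken only in patients not in atrial fibrillation (14.2.4). PASP is calculated from the peak tricuspid regurgitant (TR) velocity (14.2.5). The protocol gives no reason for cutting at the median and names no continuous interaction term.

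**The concern.** A median split treats a patient 1 mmHg above the median like one 30 mmHg above it, and treats patients just either side of the median as different in kind. If the benefit grows gradually with LV mass or PASP, that discards information. The cut value is also unknown until enrolment ends.

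The protocol makes the interaction p-value the test of whether a subgroup result is more than exploratory, and it sets that bar at 0.001. A lossy scale combined with a strict bar lowers the chance that real effect modification meets the plan's own criterion, for two of the factors the protocol considers most likely to matter.

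**Working it through.** **Inputs from the protocol**
- SD of the change in peak VO2: "SD of ΔVO_2 =2.5 ml/kg/min" (18.1.1)
- Design effect 1.2 ml/kg/min, about 215 patients enrolled, 25% missing data allowed (18.1.1)
- 1:1 allocation (section 6)
- 132 sinus-rhythm patients for MRI, 106 after 20% missing (18.1.4)
- Interaction level: two-sided 0.001, critical value 3.291 (18.2 and 18.2.1)

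**Assumptions.** The protocol gives no interaction size and no distribution for either modifier. The gradient b (change in treatment effect per SD of the modifier), normality and linearity are therefore assumed.

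**1. The plan's own figure.** The sizing uses a "two sample t-test and a two-sided alpha of 0.05 is shown in the table assuming 85% and 90% power". For effect 1.2, SD 2.5 and 85% power, the normal approximation gives 2 × (1.960 + 1.036)² × 2.5² / 1.2² = 77.9, so 78 per arm and 156 in total. The exact t calculation gives 158, as in the table. Then 158 / 0.75 = 211, consistent with about 215. In the other direction, 215 × 0.75 gives 161 analysed.

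**2. Information kept by the split.** The relative efficiency is the squared correlation between the modifier and its above-median indicator. For a normal modifier this is 2/π = 0.637, so 36.3% is lost and equal power needs π/2 = 1.57 times the patients. With a linear gradient and other shapes, the loss is 25% (uniform), about 41% (gamma with shape 4, or lognormal with sigma 0.3), 48% (lognormal with sigma 0.5) and 50% (Laplace).

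**3. Power by formula, n = 161, b = 1.2**
- Continuous: SE = 2 × 2.5 / √161 = 0.394. The ratio is 1.2 / 0.394 = 3.05. Power = Φ(3.05 − 3.291) = 40%.
- Split: the difference between halves is 2 × √(2/π) × 1.2 = 1.91, with SE = 4 × 2.5 / √161 = 0.788. The ratio is 2.43. Power = Φ(2.43 − 3.291) = 19%.

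**4. Power by simulation.** Ordinary least-squares interaction t-tests give values a few points lower, and I rely on these where both exist.

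| n | Gradient per SD | Method | Continuous | Split |
|---|---|---|---|---|
| 161 | 0.6 | formula | 4% | 2% |
| 161 | 0.9 | formula | 16% | 7% |
| 161 | 1.2 | simulation | 37% | 16% |
| 160 | 1.5 | simulation | 65% | 34% |
| 106 | 1.2 | simulation | 18% | 7% |
| 106 | 1.5 | simulation | 37% | 16% |

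All are at the 0.001 level. A gradient of 1.2 around an average effect of 1.2 means no effect at −1 SD and 2.4 at +1 SD.

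**5. What the split can detect.** For 80% power at 0.001, the effects in the two halves must differ by (3.291 + 0.842) × 4 × 2.5 / √n. That is 3.3 ml/kg/min at n = 160 and 4.0 at n = 106, against a whole-trial design effect of 1.2.

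**6. If the truth is a step.** With a step of 2.4 ml/kg/min at the median and n = 161, simulated power at 0.001 is 31% split against 17% continuous. With the same step at the 75th percentile it is 3% split against 8% continuous.

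**The case against.** **Shape.** The 36% rests on linearity, and the advantage reverses for a step near the median, as step 6 shows. The protocol's own evidence is partly reported by threshold. In Appendix 3 (2C4), an acute dose raised peak VO2 only in systolic heart failure patients with mean PA pressure above 25 mmHg. In 2C2, the dose trend in walk distance appeared below a baseline of 325 m. This stands as a caution against treating linearity as certain. It does not support the median, which need not fall near any such value.

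**The bar, not the split.** A reader might infer that the median split is why these tests would fail. The documents do not support that: the 0.001 level is a deliberately conservative choice, and the continuous test also usually misses it at moderate gradients (16% power at 0.9 per SD, 4% at 0.6). The split makes a weak test weaker.

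**Sample size.** The figure of 161 is an upper bound for PASP, which needs a measurable TR velocity, and is too large for LV mass. Even 106 reflects missing LV mass data rather than missing week-24 peak VO2. Applying the 25% allowance to 132 gives 99.

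**Left to the analysis plan.** Section 18.2 promises a separate plan, and nothing here forbids a continuous term. That is fair. But the protocol does state the comparison it intends, and that comparison is the median split.

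**Later trial.** A reader might also infer that the split spoils entry limits for a follow-on trial. Section 18.1.1 says only that a larger outcome trial may be warranted. It does not say these subgroups would set its entry criteria, so no weight is put on that.

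**Conclusion.** The point holds as a cheap improvement to a stated method. The protocol fixes an inefficient scale for two modifiers it considers important and gives no reason for it. Under a normal modifier and a linear gradient the loss is about 36% of the interaction information, or about 25% to 50% across the other shapes examined. At an assumed 1.2 ml/kg/min per SD, moving to the continuous scale roughly doubles the chance of meeting the 0.001 criterion: from about 16% to 37% at n = 161, and from about 7% to 18% at n = 106.

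The 36% is conditional and should not be read as a fixed property of this trial. For small gradients neither test is useful, and for a step near the median the split is the better test. The analyses are exploratory by default, and the primary test and sample size are untouched.

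**What to change.** In section 18.7, and in the matching list in section 2:

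- State that the interaction test for LV mass index and for PASP is the treatment-by-modifier term with the modifier continuous, added to the section 18.5 model that already contains treatment and baseline peak VO2. Apply the 0.001 criterion to that term.
- Fix the scale of each modifier in advance (for example, log or untransformed) rather than choosing it from the data.
- Report the treatment effect with 95% CI across the modifier range, with a plot or spline term to check linearity.
- Keep the above- and below-median estimates for display only.

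The cost is a few sentences and no new data. The downside is reliance on a roughly linear change in effect, which the plot or spline is there to examine.

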9. TREATMENT INTERVENTIONS

9.1 Intervention

The therapeutic intervention is double blinded therapy with placebo or the PDE-5 inhibitor sildenafil (as Revatio[®]). Study drug therapy will be given for 24 weeks starting with 20 mg by mouth three times a day (tid) for 12 weeks. If that dose is well tolerated, the dose will be increased to 60 mg tid at week 12 for the remaining 12 weeks of the study. Patients unable to tolerate the 60 mg tid will be maintained on the 20 mg tid dose. The active and placebo study medication will appear identical to preserve the double blind design of the study. If patients develop side effects thought potentially related to study drug (including but not limited to headache, flushing, dizziness, orthostatic lightheadedness, dyspepsia, nasal congestion, diarrhea, rash, visual disturbance), the dose will be adjusted to the previously tolerated dose. As recommended for patients with HF, patients will be encouraged to weigh daily and record weights. If patients have experienced enhanced responsiveness to their diuretic dosage (decreased weight *and* symptoms of over-diuresis such as lightheadedness), consideration can be given to reducing the diuretic dose rather than the study drug.

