9.2 Control Group

The control group in this study will include patients randomized to placebo medication. Study drug (sildenafil or placebo) will be given in a double blind fashion and all patients will undergo identical study procedures including dose titration.

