Therefore, we initiate therapy with 20 mg tid recognizing the probable advanced age of study participants, up-titrate therapy at 12 weeks in the absence of side-effects, down titrate if increasing the dosage results in side effects but use a goal dose consistent with that providing the maximal hemodynamic effect in humans with PH and equivalent to that producing the observed myocardial effect in the mouse. Selection of this strategy provides the opportunity to maximize efficacy while minimizing side effects in this population.

At the study visits where the first dose of study drug (20 mg) is administered or the higher dose (60mg) is administered, systemic blood pressure measurement will be obtained in sitting and standing position one hour after administration of study drug. The dose of study drug will be stopped (therapy initiation visit) or reduced (therapy up-titration visit) in any patient in whom the SBP (seated or standing) measured 1 hour after the study drug during the drug initiation/titration visit is < 100 mm Hg or DBP < 40 mm Hg. Patients with chest pain, palpitations, diaphoresis will have a 12-lead ECG and a clinical evaluation as soon as possible. Study drug will be stopped in patients with acute coronary syndromes, AV block, or life-threatening arrhythmias.

At all study visits (in person or phone follow up), monitoring for toxicity will include questioning and encouragement to call the investigator about headache, flushing, dizziness, orthostatic lightheadedness, dyspepsia, nasal congestion, diarrhea, rash, visual disturbance, chest pain, palpitations, worsening dyspnea, peripheral edema, diaphoresis, tinnitus or hearing loss. On every study visit, investigators will obtain a medical history and perform a targeted cardiovascular physical examination. After each dose initiation or dose escalation, study coordinators will contact the patient by phone at 1 and 2 days after the dosing visit to monitor for adverse effects.

9.5.1 Potential for enhanced diuretic responsiveness:

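### Dose of sildenafil achieved is settled after randomization, so the pre-specified subgroup comparison on it is not randomized and can be biased by selection in either direction

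*Protocol*

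**What the plan says.** Section 18.7 opens its list with "Pre-specified subgroup analysis will include comparison of the effect of therapy in patients with" and names five factors. Two are expressly fixed at baseline, for example "LV mass index above and below the median at entry into the study". The third is "Dose of sildenafil achieved". Section 2 carries the same list.

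The dose reached is settled later. Section 9.1 says of the starting dose: "If that dose is well tolerated, the dose will be increased to 60 mg tid at week 12", and then "Patients unable to tolerate the 60 mg tid will be maintained on the 20 mg tid dose". Section 9.5 adds a blood pressure rule applied one hour after dosing: "The dose of study drug will be stopped (therapy initiation visit) or reduced (therapy up-titration visit) in any patient in whom the SBP" (or the diastolic pressure) is below a stated limit. Placebo patients go through the same blinded process: "all patients will undergo identical study procedures including dose titration" (section 9.2). The protocol does not say whether placebo patients are to be classified by their sham dose or pooled as one comparator.

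The decision rule for all subgroups is in section 18.2.1: "subgroup analyses will be considered exploratory unless the p-value from an interaction test is smaller than 0.001".

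**The concern.** A subgroup comparison of the treatment effect keeps the protection of randomization only if the factor is fixed before treatment starts. Dose achieved is a response to study drug. If sildenafil provokes more intolerance than placebo, the sildenafil patients who stay at the higher level are a more strongly selected group than the placebo patients who do. The same holds, in mirror image, at the lower level. If tolerance is related to how exercise capacity would have changed anyway, the arms differ within each level even when the drug does nothing.

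A stricter significance threshold does not repair this. It controls how often chance alone yields a small p-value and leaves the selection in place. As written, an interaction on this factor with p below 0.001 would cease to be merely exploratory.

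The protocol's own background shows how such a table can mislead. Appendix 3, section 2C6 describes a systolic heart failure study with uptitration as tolerated. Baseline peak VO2 was 10.8 in patients at the lowest dose (n=7), against 13.9 and 12.7 at the two higher doses (n=4 each). The groups are tiny, but they already differed before treatment, and the appendix reads the result as a trend with dose.

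**Working it through.** **The plan's own figure.** Section 18.1.1 gives 158 evaluable patients for a difference of 1.2 ml/kg/min, SD 2.5, 85% power and two-sided 0.05. By the normal approximation, n per arm = 2 × (1.960 + 1.036)² × 2.5² / 1.2² = 77.9, so 78 per arm or 156 in total; the t-test adds about 2. The figure reproduces. It supplies the SD (2.5), the yardstick (1.2) and the arm size (79) used below.

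**Assumptions, because the protocol gives no values.** True drug effect zero; a latent tolerance score, standard normal, with correlation r with the change in peak VO2; a patient reaches the higher level if the score exceeds a cut-off. Illustrative proportions reaching it: 70% on sildenafil, 95% on placebo. r = 0.3 to 0.5.

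**Formula.** If a proportion p reaches the higher level and φ is the normal density at the cut-off, the mean tolerance score is φ/p among those who reach it and −φ/(1−p) among those who do not.
- Sildenafil, p = 0.70: φ = 0.3477; means +0.497 and −1.159.
- Placebo, p = 0.95: φ = 0.1031; means +0.109 and −2.063.

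The false effect in a group is 2.5 × r × (sildenafil mean − comparator mean).

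**(a) Placebo split by sham dose.**
- High stratum: 2.5 × r × (0.497 − 0.109) = 0.29 (r = 0.3) to 0.49 (r = 0.5).
- Low stratum: 2.5 × r × (−1.159 + 2.063) = 0.68 to 1.13.
- High minus low: −0.39 to −0.64. Both strata look beneficial, the lower one more so.

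Varying the sildenafil proportion, with placebo at 95%:

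| Reach higher level on sildenafil | High stratum | Low stratum |
|---|---|---|
| 80% | 0.18-0.30 | 0.50-0.83 |
| 70% | 0.29-0.49 | 0.68-1.13 |
| 60% | 0.40-0.67 | 0.82-1.37 |

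If the two arms have equal proportions, the two means in each stratum are equal and the bias under this model is zero.

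**(b) Each sildenafil dose group against all placebo.** The placebo mean is 0.
- High group: 2.5 × r × 0.497 = 0.37 to 0.62.
- Low group: 2.5 × r × (−1.159) = −0.87 to −1.45.
- High minus low: 2.5 × r × 1.656 = 1.24 to 2.07.

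This version does not need a difference in tolerance between arms. With 10% intolerant in both, the spurious difference is still 1.46 at r = 0.3.

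**False interactions at p < 0.001** (simulation, 79 per arm, no drug effect). Under (a), with 10-40% of sildenafil and 10% of placebo patients not reaching the higher level, the rate was 0.0007 to 0.0013, close to nominal. Under (b), with 70% of sildenafil patients reaching it, the high-versus-low comparison passed in about 10% of trials at r = 0.3 and 58% at r = 0.5.

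**The case against.** The strongest reply has four parts.

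*The harm is limited by design.* Subgroup results are exploratory by default and the primary analysis is intention-to-treat. Both points stand, and they keep this away from the trial's main conclusion.

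*The numbers are assumed.* They are. The protocol gives no rate of reaching the higher level in either arm, and its evidence on tolerability is mixed. Section 9.4 reports no dose response for tolerability in the pulmonary hypertension trial, and section 9.5 reports fewer discontinuations for side effects on active drug than on placebo in the erectile dysfunction meta-analysis. Against that, Appendix 3 has only 27% reaching the top dose in the small systolic heart failure study. Equal tolerance would remove the bias in version (a), though not in version (b).

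*The handling of placebo may be fixed in the analysis plan.* Possibly. But the protocol itself names the factor, calls it pre-specified and attaches the decision rule, and neither way of handling placebo restores a randomized comparison.

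*A reader might infer more than this supports.* It is tempting to say that the analysis will manufacture a benefit at the higher dose. That follows only if placebo is pooled; with placebo split by sham dose, the same model favours the lower dose. It is also tempting to say that the 0.001 rule will let a false result through. Under the split version the false-positive rate stays near nominal, so the harm there is misleading estimates in each stratum. Finally, the protocol does not say the trial is meant to choose the dose for a larger study. Section 18.1.1 ties such a study to benefit on exercise and mechanisms, and section 9.4 promises only exploratory dose-response data.

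**Conclusion.** The point holds as a matter of design and needs no figure. A factor determined after randomization by tolerance and blood pressure on study drug stands in a list of subgroups for the treatment effect, under a rule that addresses chance and not selection.

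Direction and size cannot be known from the protocol. With SD 2.5, no drug effect, 70% against 95% reaching the higher level and r of 0.3 to 0.5, the distortion of the high-minus-low contrast runs from −0.39 to −0.64 ml/kg/min if placebo is split by sham dose, and from +1.24 to +2.07 if it is pooled. The planned effect is 1.2. That the sign turns on a choice the protocol does not state is itself a reason not to treat this as a subgroup analysis. The primary intention-to-treat result is not affected.

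**What to change.** Delete item 3 from the subgroup lists in sections 2 and 18.7, so that the interaction test and the 0.001 rule apply only to factors defined at baseline. Report outcome by dose achieved as a descriptive table within the sildenafil arm, labelled non-randomized.

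The between-arm change from week 12 to week 24 may also be reported, as a randomized comparison of drug with placebo over the escalation period. It should carry the statement that dose is confounded with duration of exposure, since every patient is scheduled to escalate at the same visit. It therefore does not isolate a dose effect.

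The cost is one list item removed in two places and one descriptive table kept. Sample size, visits and the primary analysis do not change.
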